### 2.1.2 Exclusion Criteria

- 2.1.2.1 Treatment with an investigational drug study within 28 days of before starting on study treatment.
- 2.1.2.2 Subjects with concurrent cytotoxic chemotherapy or radiation therapy. There must be at least 28 days between any other prior chemotherapy (or radiotherapy) and study treatment. Prior antibody therapy must be discontinued 8 weeks prior to start of study treatment. Prior hormonal therapy can be discontinued 24 hours prior to start of study treatment.
- 2.1.2.3 Any prior PSA, MUC1, and/or brachyury-targeted immunotherapy (e.g., vaccine) must have been discontinued at least 12 weeks before initiation of study treatment. Subjects must have recovered from all acute toxicities from prior treatment prior to screening for this study.
- 2.1.2.4 Prior treatment with Adenovirus-Based vectors immunotherapy
- 2.1.2.5 Known active brain or central nervous system metastasis, or seizures requiring anticonvulsant treatment, cerebrovascular accident, or transient ischemic attack (< 6 months prior to enrollment).
- 2.1.2.6 Subjects with a history of autoimmune disease (active or past), such as but not restricted to inflammatory bowel disease, systemic lupus erythematosus, ankylosing spondylitis, scleroderma, or multiple sclerosis. Autoimmune-related thyroid disease, type I diabetes and vitiligo are permitted if the condition is well controlled.
- 2.1.2.7 Subjects with serious intercurrent chronic or acute illness, such as cardiac or pulmonary disease, hepatic disease, or other illness considered by the Investigator as high risk for investigational drug treatment.
- 2.1.2.8 Subjects with a history of heart disease, such as congestive heart failure (class II, III, or IV defined by the New York Heart Association functional classification), history of unstable or poorly controlled angina, or history (< 1 year prior to enrollment) of ventricular arrhythmia.
- 2.1.2.9 Subjects with a medical or psychological impediment that would impair the ability of the subject to receive therapy per protocol or impact ability to comply with the protocol or protocol-required visits and procedures.
- 2.1.2.10 Presence of a known active acute or chronic infection, including human immunodeficiency virus (HIV, as determined by enzyme-linked immunosorbent assay [ELISA] and confirmed by western blot) and hepatitis B and hepatitis C virus (HBV/HCV, as determined by HBsAg and hepatitis C serology).
- 2.1.2.11 Subjects on systemic intravenous or oral steroid therapy (or other immunosuppressive, such as azathioprine or cyclosporin A) are excluded on the basis of potential immune suppression. Subjects must have had at least 6 weeks of discontinuation of any steroid therapy (except that used as premedication for chemotherapy or contrast-enhanced studies) prior to enrollment. Physiologic (replacement) doses od steroids as well as nasal, topical or inhaled steroids are allowed.
- 2.1.2.12 Subjects with known allergy or hypersensitivity to any component of the investigational

product will be excluded.

- 2.1.2.13 Subjects with acute or chronic skin disorders that will interfere with injection into the skin of the extremities or subsequent assessment of potential skin reactions will be excluded.
- 2.1.2.14 Subjects vaccinated with a live (attenuated) vaccine (e.g., FluMist®) or a killed (inactivated)/subunit vaccine (e.g., PNEUMOVAX®, Fluzone®) within 28 days or 14 days, respectively, of the first planned dose of ETBX vaccine.
- 2.1.2.15 Patients with second malignancy within 3 years of enrollment; Patients curatively treated non-melanoma skin cancers or carcinoma in situ of the bladder, are not excluded.
- 2.1.2.16 Use of herbal products that may decrease PSA levels (e.g. saw palmetto)
- 2.1.2.17 Patients who have received radiation therapy, radionuclide therapy or undergone surgery within certain duration (4 weeks) of enrollment

### 2.1.3 Recruitment Strategies

This study will be listed on available websites (www.clinicaltrials.gov, https://ccr.cancer.gov/clinical-trials-search-start) and participants will be recruited from the current patient population at NIH.

#### 2.2 SCREENING EVALUATION

Confirmation of diagnosis by NCI Laboratory of Pathology or Walter Reed National Military Medical Center (at any time prior to enrollment). If no tissue is available, a pathologist's report documenting histological diagnosis of prostate cancer along with a clinical course consistent with the disease may be used.

Studies should be done within 28 days prior to enrollment unless otherwise noted below.

- History and physical exam including ECOG performance status, height, weight and vital signs
- 12-lead EKG
- Scans
  - CT CAP (chest abdomen and pelvis) with oral and IV contrast (MRI abdomen/pelvis with contrast + chest CT without contrast if IV contrast is contraindicated or CT CAP is inadequate)
  - Bone scan
- Clinical laboratory tests (within 16 days prior to enrollment)
  - Hepatic Panel (Alkaline Phosphatase, ALT/GPT, AST/GOT, Total Bilirubin, Direct Bilirubin)
  - Acute Care Panel (Sodium [NA], Potassium [K], Chloride [CL] Total CO2 [Bicarbonate], Creatinine, Glucose, Urea nitrogen, eGFR)
  - CBC with differential
  - Urinalysis (24-hour collection will be done as needed)
  - Serum PSA
  - Testosterone level
  - PT/INR, PTT

- HBV (HBsAg), HCV (anti-HCV), HIV (anti-HIV) screening (within 3 months prior to enrollment)
- Appropriate tumor imaging and assessment. All baseline tumor measurements should be performed based on the subject's qualifying scan obtained within 28 days prior to the start of treatment.

### 2.3 REGISTRATION PROCEDURES

Authorized staff must register an eligible candidate with NCI Central Registration Office (CRO) within 24 hours of signing consent. A registration Eligibility Checklist from the web site (http://home.ccr.cancer.gov/intra/eligibility/welcome.htm) must be completed and sent via encrypted email to: NCI Central Registration Office [contact]. After confirmation of eligibility at Central Registration Office, CRO staff will call pharmacy to advise them of the acceptance of the patient on the protocol prior to the release of any investigational agents. Verification of Registration will be forwarded electronically via e-mail to the research team. A recorder is available during non-working hours.

### 2.3.1 Treatment Assignment Procedure

### Cohorts

Nu	ımber	Name	Description
1		Dose De-Escalation	Subjects enrolled to dose de-escalation cohorts
2		Dose Expansion	Subjects enrolled at the MTD after the MTD is established

#### Arms

Number	Name	Description
1	Dose De-Escalation	ETBX-071; adenoviral PSA vaccine + ETBX-061; adenoviral MUC1 vaccine + ETBX-051; adenoviral brachyury vaccine dose de-escalation
2	Dose Expansion	ETBX-071; adenoviral PSA vaccine + ETBX-061; adenoviral MUC1 vaccine + ETBX-051; adenoviral brachyury vaccine

## Stratifications

None

## **Randomization and Arm Assignment**

Not a randomized study. Subjects in Cohort 1 will be assigned to Arm 1; subjects in Cohort 2 will be assigned to Arm 2.

2.4 BASELINE EVALUATION

All subjects are required to complete baseline evaluations within 1 day prior to the first planned dosing of the study drug (Any screening evaluation done on D-1 of treatment can also serve for

the baseline evaluation). The following procedures and evaluations will be performed and documented in the subject's source records.

- History and physical exam, including weight, ECOG status and vital signs
- Hepatic Panel (Alkaline Phosphatase, ALT/GPT, AST/GOT, Total Bilirubin, Direct Bilirubin)
- Acute Care Panel (Sodium [NA], Potassium [K], Chloride [CL] Total CO2 [Bicarbonate], Creatinine, Glucose, Urea nitrogen, eGFR)
- CBC with differential
- PSA and testosterone

If these assessments have been previously performed within 24 hours prior to the first dosing, a second assessment at baseline/week 0 can be omitted.

## **3 STUDY IMPLEMENTATION**

## 3.1 STUDY DESIGN

This is a Phase I trial in subjects to test the safety of 3 different adenovirus based vaccines (ETBX-051, ETBX-61, ETBX-71) administered to patients with metastatic castration resistant prostate cancer at the same time. All vaccines utilize the same second generation E1(-), E2 (-) vector.

ETBX-071 is a PSA-targeting vaccine that comprises the Ad5 [E1-, E2b-] vector containing a PSA gene insert. The investigational product ETBX-061 is a MUC1-targeting vaccine that comprises the Ad5 [E1-, E2b-] vector containing a modified MUC1 (MUC1c) gene insert. The investigational product ETBX-051 is a brachyury-targeting vaccine that comprises the Ad5 [E1-, E2b-] vector containing a modified brachyury gene insert.

## **Table 2: Investigational Products**

Tabl	e 2a

Product Name(s):	ETBX-071 (Ad5 [E1-, E2b-]-PSA Vaccine)	
Dosage Form:	Suspension for injection	
Dose	$5 \times 10^{11}$ VP (standard dose), $1 \times 10^{11}$ VP (DL-1), or $5 \times 10^{10}$ VP (DL-2).	
Route of Administration	SC injection	
Physical Description	ETBX vaccine is supplied as a sterile, clear solution in a 2-mL single- dose vial. The vaccine is provided at a concentration of 5 x $10^{11}$ VP per 1 mL and contains ARM formulation buffer (20 mM TRIS, 25 mM NaCl, 2.5% glycerol, pH 8.0). Each vial contains approximately 1.1 mL of the vaccine. The product should be stored at $\leq$ -20°C.	
Manufacturer	Etubics	

Table 2b

Product Name(s):	ETBX-061 (Ad5 [E1-, E2b-]-MUC1 Vaccine)	
Dosage Form:	Suspension for injection	
Dose	$5 \times 10^{11}$ VP (standard dose), $1 \times 10^{11}$ VP (DL-1), or $5 \times 10^{10}$ VP (DL-2).	
Route of Administration	SC injection	
Physical Description	ETBX vaccine is supplied as a sterile, clear solution in a 2-mL single- dose vial. The vaccine is provided at a concentration of 5 x $10^{11}$ VP per 1 mL and contains ARM formulation buffer (20 mM TRIS, 25 mM NaCl, 2.5% glycerol, pH 8.0). Each vial contains approximately 1.1 mL of the vaccine. The product should be stored at $\leq$ -20°C.	
Manufacturer	Etubics	

#### Table 2c

Product Name(s):	ETBX-051 (Ad5 [E1-, E2b-]-Brachyury Vaccine)	
Dosage Form:	Suspension for injection	
Dose	$5 \times 10^{11} \text{ VP}$ (standard dose), $1 \times 10^{11} \text{ VP}$ (DL-1), or $5 \times 10^{10} \text{ VP}$ (DL-2).	
Route of Administration	SC injection	
Physical Description	ETBX vaccine is supplied as a sterile, clear solution in a 2-mL single- dose vial. The vaccine is provided at a concentration of 5 x $10^{11}$ VP per 1 mL and contains ARM formulation buffer (20 mM TRIS, 25 mM NaCl, 2.5% glycerol, pH 8.0). Each vial contains approximately 1.1 mL of the vaccine. The product should be stored at $\leq$ -20°C.	
Manufacturer	Etubics	

The vaccines will be administered subcutaneously (SC) in 3 separate injections every 3 weeks for 3 immunizations (there are no booster injections in dose escalation cohort). It is preferred to administer the injections in the anterolateral section of the same thigh separated from each other by a minimum of 5 cm. It is also preferred to administer ETBX-071 most proximal, ETBX-061 in the middle, and ETBX-051 most distal and the injected thigh should be alternated each treatment visit when possible. In the dose expansion cohort, ETBX-051, ETBX-61, ETBX-71 vaccines will be administered on Weeks 0, 3, and 6 for a total of three injections followed by booster injections every 8 weeks for 1 year.

## **3.1.1** Dose Limiting Toxicity

A dose limiting toxicity (DLT) is defined as occurring within 28 days after the first vaccine administration and meeting any of the below criteria:

- Any Grade 3 or greater toxicity as defined by National Cancer Institute (NCI) Common Terminology Criteria for Adverse Events (CTCAE) Version 5 that is possibly, probably, or definitely related to the vacines with the exception of transient (≤ 24 hours) Grade 3 flu-like symptoms or fever, which is controlled with medical management or transient (≤ 24 hours), Grade 3 fatigue, local skin reactions or rash, headache, nausea, emesis that resolves to Grade ≤ 1 or laboratory abnormalities that are not associated with organ pathology.
- Any Grade 2 or higher autoimmune reaction (except endocrine-related immune toxicity) or immediate hypersensitivity reaction. Any grade 3 autoimmune endocrine-related toxicity that has not resolved clinically within 7 days of initiating therapy will also be defined as a DLT.
- Generalized erythroderma or macular or papular rash lasting less than 7 days and not associated with desquamation will not be DLTs.
- For purposes of dose de-escalation the DLT evaluation period will be for 1 week following the first dose of drug.
- Subjects experiencing a DLT will be removed from protocol therapy.

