3.3 Dose Modifications and Delays

# 3.3.1 Dosing Delay (applies to events occurring outside of the DLT evaluation period)

Patients must have recovered to  $\leq$  grade 2 for injection site reaction or grade  $\leq$  1 for any other toxicity related to the vaccines for the parameters used to assess levels of organ function required for eligibility (see Section 2) after each vaccination in order to receive a subsequent vaccination (see Sections 2.1.1.7 and 2.1.1.8).

If  $\geq$  grade 3 nonautoimmune toxicity attributable to the vaccines persists for > 42 days, the patient will not receive further vaccine inoculations and will be removed from the protocol treatment and followed for resolution of toxicity and immune/survival endpoints.

Patients who develop grade 3 injection site reactions will have their vaccines held until injection site reaction resolves to grade 2 or less. Patients will receive a diary card to record injections site reactions (see **Appendix B**).

Patients who develop  $\geq$  a grade 2 allergic or autoimmune disease that threatens vital organ function or any  $\geq$  grade 3 autoimmunity, not related to a therapeutic response, will be removed from the protocol treatment and followed for resolution of toxicity and immune/survival endpoints.

Patients who develop any grade 4 toxicity attributable to the vaccines will be removed from the protocol treatment and followed for resolution of toxicity and immune/survival endpoints.

For unrelated acute illnesses present at the time of a scheduled vaccination, dosing can be delayed until symptoms subside, or the subject may be withdrawn at the discretion of the Investigator; delays up to 4 weeks are considered acceptable in this setting.

If a scheduled vaccine dose is missed due to scheduling or logistical issues, the vaccine may be given within 7 days of the appointed time.

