# **3.5.1** Criteria for removal from protocol therapy

- Completion of protocol therapy.
- Clinical or radiographic progression of disease (not including PSA progression). Patients with serological progression alone will remain on treatment at the discretion of the PI.
- Unacceptable Toxicity as listed in section **3.3.1**
- Any serious adverse event that is unexpected relative to the known safety profile of the investigational agents in the opinion of the investigator
- Participant requests to be withdrawn from active therapy
- Investigator discretion

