# 8.4.6.2 Halting Guidelines

# The following safety events will trigger a temporary suspension of the study injections:

- Death possibly related to the study agent.
- Two Grade 4 toxicity events that are possibly related to the study agent.
- At any time during the expansion phase > 33% of subjects experience a Grade 3 or 4 major organ toxicity possibly related to study injections.

Assessment of these halting rules is a review of cumulative events for all study participants and should not be confused with reasons for delaying or terminating the treatment schedule of any individual subject.

Treatment may also be suspended for safety concerns other than those described above if, in the judgment of the Investigator, participant safety is threatened.

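### Section 3.1.1 gives conflicting DLT rules for a short-lived Grade 3 rash, and its rash exemption has no grade cap

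*Combined protocol and SAP*

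**What the plan says.** All of this is in the combined protocol and SAP.

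- **Lead-in to 3.1.1.** A DLT is an event within 28 days of the first vaccination "and meeting any of the below criteria". One criterion is enough.
- **First bullet.** Any toxicity of Grade 3 or greater that is at least possibly related is a DLT. Among the exceptions are transient events (24 hours or less) listed as "Grade 3 fatigue, local skin reactions or rash, headache, nausea, emesis that resolves to Grade" 1 or lower. The rash exception is thus limited by grade, duration and resolution.
- **Second bullet.** A Grade 2 or higher autoimmune reaction (endocrine events apart) or immediate hypersensitivity reaction is a DLT.
- **Third bullet.** "Generalized erythroderma or macular or papular rash lasting less than 7 days and not associated with desquamation will not be DLTs". It names no grade and does not mention the first or second bullet.
- **Last bullet.** "Subjects experiencing a DLT will be removed from protocol therapy".

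Section 8.4.4 sends the reader back to Section 3.1 for the definition. Section 8.3.1 says who is evaluable for DLT, not what a DLT is. Neither settles the overlap.

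**The concern.** Two bullets of one definition give opposite answers for the same patient, so two careful investigators could classify the same rash differently. The authors limited the rash exception in the first bullet to Grade 3 but put no grade limit in the third.

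The DLT fraction is one of the primary endpoints in 8.1.1, and the DLT count drives the dose rule in 3.1.2. At most one DLT in six leads to expansion, with 12 more subjects at that dose; two or more lead to de-escalation. With one other DLT in the cohort, a single rash decides which. Section 1.2.10 states that the three-vaccine combination has not been tested in humans.

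**Working it through.** **1. The bullets side by side.** Take a vaccine-related macular or papular rash, or generalized erythroderma, without desquamation.

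| Event | First bullet | Third bullet |
|---|---|---|
| Grade 3, 24 hours or less, resolves to Grade 1 or lower | Not a DLT (if the exception is not confined to local rash) | Not a DLT |
| Grade 3, more than 24 hours, less than 7 days | DLT | Not a DLT |
| Grade 4, less than 7 days | DLT | Not a DLT (no cap) |
| Grade 3 or higher, 7 days or more | DLT | Does not apply |

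The second row is the direct conflict. The third row follows only if the third bullet overrides the first. Desquamating rash is unaffected.

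**2. The plan's own threshold.** Section 8.4.4 calls a dose safe if fewer than 33% of subjects have a DLT, given as 0 of 3 or at most 1 of 6. This reproduces: 0/3 = 0% and 1/6 = 16.7% pass; 2/6 = 33.3% does not.

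**3. When one classification decides.** Suppose one of six subjects has such a rash and no other DLT. The classification decides if exactly one of the other five has a DLT. At an assumed other-DLT rate of 5% this is 5 × 0.05 × 0.95^4 = 0.204. At 10% it is 5 × 0.10 × 0.90^4 = 0.328.

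**4. How often such a rash might occur.** The documents give no rate for this combination. Section 11.1.2, on the earlier single-vaccine trial (ETBX-011), reports no dose limiting toxicity. Its table of Grade 3-4 events, based on 34 patients, lists no rash. The table shows events in at least 2% of patients, and one event in 34 is 2.9%, so a single case would have appeared.

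- One-sided 95% upper bound for 0/34: 1 − 0.05^(1/34) = 8.4%.
- Only 6 of those patients received 5×10^11 VP. For 0/6 the bound is 1 − 0.05^(1/6) = 39.3%.

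Both bounds cover all Grade 3-4 rash. The affected subset is narrower.

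**5. Effect on the cohort decision.** The chance of at most one DLT in six is (1 − p)^6 + 6p(1 − p)^5. Here p is the other-DLT rate alone if the rash is exempt, and that rate plus the rash rate if it counts. All rates are assumptions and are taken as additive. Example, other DLTs 5% and rash 2%: 0.93^6 + 6 × 0.07 × 0.93^5 = 0.6470 + 0.2922 = 0.9392.

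| Other DLTs | Rash exempt | Counted, rash 1% | Rash 2% | Rash 5% | Rash 8.4% |
|---|---|---|---|---|---|
| 0% | 100% | 99.9% | 99.4% | 96.7% | 91.6% |
| 5% | 96.7% | 95.4% | 93.9% | 88.6% | 81.3% |
| 10% | 88.6% | 86.6% | 84.4% | 77.6% | 69.5% |

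At rash rates of 1-2% the drop is 0.1-0.6 points (other DLTs 0%), 1.3-2.8 points (5%) and 2.0-4.1 points (10%). The table compares all such rash exempt with all such rash counted. It illustrates the Grade 3 conflict, not the effect of a Grade 4 cap.

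**The case against.** **Precedence may be settled already.** The third bullet is the specific, categorical sentence, so it can be read as a carve-out from the first. That is the natural reading, and on it the Grade 3 conflict goes away. But the lead-in lets any one criterion suffice, and nothing says the third bullet overrides. The two problems are alternatives: read literally, the bullets conflict at Grade 3; read as a carve-out, the exemption has no cap.

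**The Grade 4 case may be empty.** Grades come from CTCAE version 5, which the documents do not reproduce. Whether a short, non-desquamating rash of this kind can reach Grade 4, and how often, cannot be checked here. This stands. The Grade 4 point is only a literal consequence of the missing cap.

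**Other rules would catch a serious event.** A reader might infer that a patient with a Grade 4 rash would stay on treatment unchecked. The documents do not support that.

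- Section 3.3.1 says "Patients who develop any grade 4 toxicity attributable to the vaccines will be removed from the protocol treatment". Its heading limits it: "applies to events occurring outside of the DLT evaluation period". However, 3.5.1 lists the toxicities in 3.3.1 as grounds for removal without repeating that limit. Moreover, the fourth bullet of 3.1.1 gives one week as the evaluation period for de-escalation, and on that reading 3.3.1 applies from then on.
- Section 3.5.1 also allows removal at investigator discretion and for "Any serious adverse event that is unexpected relative to the known safety profile of the investigational agents".
- Section 8.4.6.2 suspends injections after "Two Grade 4 toxicity events that are possibly related to the study agent" and lets the investigator suspend for other safety concerns.
- Safety data are examined after six patients (8.4.6.1), and AEs and SAEs are themselves primary endpoints (8.1.1), so the event would still be reported.

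These safeguards protect the patient. None of them puts the event into the DLT count.

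**The second bullet also overlaps.** The third bullet directly follows the autoimmune and hypersensitivity criterion and could be read as qualifying that too. This stands, and the fix has to cover it.

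**Conclusion.** Wrong as written, and minor. Section 3.1.1 contains conflicting DLT rules for a related Grade 3 rash of the named types lasting more than 24 hours and less than 7 days without desquamation. If the third bullet is instead taken as a carve-out, it has no grade cap.

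The size rests on the event being rare. The single-vaccine trial makes that probable, but it does not establish it for three vaccines given together at this dose. If the event is rare, the average effect on the cohort decision is a few percentage points at most. In the particular cohort where it occurs alongside one other DLT, it decides the dose.

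A reader might take the larger contrasts in the table, such as 88.6% against 69.5%, as the cost of the missing Grade 4 cap. They are not: they use a bound for all Grade 3-4 rash and contrast full exemption with full counting. No figure in the documents measures the effect of the cap alone.

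**What to change.** Before the first subject is dosed, amend the third bullet and keep its present scope:

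- Open it with *As an exception to the first bullet*.
- Insert *of Grade 3 or lower* after the rash types, and leave the duration and desquamation conditions as they are.
- Close it with *unless it is part of a reaction that meets the second bullet*.
- Add: *Any such event of Grade 4 or higher that is at least possibly related to the vaccines is a DLT under the first bullet.*
- State that the 24-hour limit in the first bullet applies to skin reactions and rash that the third bullet does not cover.

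Two cautions on wording. Do not put *generalized* before the macular or papular rash: that would narrow the exemption and could make a localized rash a DLT while a generalized one stays exempt. Keep the relatedness condition in the Grade 4 sentence, so that unrelated events are not drawn in.

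The cost is a short amendment to 3.1.1. Sample size, visits and data collection do not change.
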